### **3.2 Proposal Geography** *Please read section 3.2 of the guidance*

- Local/Regional (relating to one or more specific areas within Scotland)
- National (relating to the whole of Scotland)
- UK-wide (relating to the whole of the UK, or to UK regions outside Scotland)
- International (relating to areas within the EEA)
- International (relating to areas beyond the EEA)

### **3.3 Proposal Duration and Frequency** *Please read section 3.3 of the guidance*

3.3.01	What is the proposed duration of the proposal?	We now requested for access to the data until 2019-12-31, for the purpose of answering a few questions of the editorial team of Lancet on the presentation of the data (e.g. adding standard deviations to data presented)
3.3.02	Does the proposal require updates of information at regular intervals? Please give details	no
3.3.03	Are you seeking approval to iterate the proposal (ie the whole project, audit or study) at regular intervals? Please give details	no

3.4 Statutory and Regulatory Context Please read section 3.4 of the guidance		
3.4.01	Does your proposal have a statutory or regulatory justification - is the proposal responding to a statutory or regulatory instruction, duty or order? Please give details	NO
3.4.02	Which Data Protection Act schedule 2 and schedule 3 conditions are relevant? (a list of conditions can be found at Appendix B )	
Schedule 2:
 
Condition 3; the use of patient identifying data is not necessary to carry out the research. The linking code can be anonymized using a random number. The researcher therefore do not need identifying data for carrying our analyses. Also the use of data which is not directly identifiable is minimized, by requesting a minimum in baseline characteristics and only data from readmissions with a relevant code.
 
Schedule 3, Condition 8:

		The processing is necessary for medical researcher, and analyses is undertaken by health professional who completed information governance training.
3.4.03	Are there any relevant information sharing agreements, protocols or contracts in place which support your proposal? Please give details and attach as supporting documentation if available	No
3.4.04	Has a Privacy Impact Assessment been carried out which supports your proposal? Please give details and attach as supporting documentation if available	Yes, see attachment. Privacy risk can be adequately eliminated.
3.4.05	Has local Caldicott approval been given for your proposal at a local level? Please give details	No
3.4.06	Are approvals from Caldicott Guardians outside Scotland pending or received? Please give details	No

3.5	Research and Ethics Governance Please read section 3.5 of the guidance	
3.5.01	Has your proposal sought research/ethics approval?	Yes
3.5.01a	If yes, please provide committee details and status of approval (ie pending, approved, etc). Please attach as supporting documentation if available	Radboud University medical Center- Institutional review board [name] [name] T [contact] E:[contact] - approved -
3.5.01b	If no, please explain why research/ethics approval is not sought:	

3.6 Safe Havens Please read section 3.6 of the guidance	
3.6.01	Do you intend to access the data requested exclusively through a safe haven listed at Appendix A ? Please provide details of which safe haven/s
3.6.02	If you applying to use NHS NSS data and you do not intend to do this through the National Safe Haven, please explain why

## Section 4 – Data & Data Subjects

### 4.1 Data yet to be collected *Please read section 4.1 of the guidance*

Not applicable

Dataset/source Name	Collection by (whom)?	Explicit consent sought? If Yes, describe how explicit consent being sought – provide copies of participant consent/registration forms, etc. If No, explain why consent is not being sought (eg impractical, risk associated with seeking consent, etc)

### 4.2 All Other Datasets / sources *Please read section 4.2 of the guidance*

Dataset/source Name	Data Controller (Organisation)	Original purpose compatible with proposal?
Scottish Morbidity Record (SMR01)	National Services Scotland	Yes
NRS Deaths	NRS	Yes
CHI Database	NHS Boards	Yes

How were individuals originally informed of the use of their data? (if known)

Project specific consent was impractical for this study because of large size of the survey group and patients are not contacted. However:

- a) no identifiable patient data will be disclosed
- b) the necessary linkage will be performed by data controllers from the NHS Scotland board, that already hold the data. After linkage the data will be anonymised.
- c) the medical research serves public interest as outlined under 3.1.07.

The final dataset for analysis will not hold data that could result in indirect identification.

For existing dataset/sources for which the data controller is not an NHSScotland board, please append evidence of the data controllers permission to use the data

### 4.3 Data Variables *Please read section 4.3 of the guidance*

Dataset/source Name	Variable	Time Period/Range	Processing only?
Anonymised ID			
Scottish Morbidity Record (SMR 01)	CHI	2004- Dec 2016	Yes
Scottish Morbidity Record (SMR 01)	Date of admission	2004- Dec 2016	No
Scottish Morbidity Record (SMR 01)	Sex	2009- Dec 2016	No
Scottish Morbidity Record (SMR 01)	Age (Date of admission- birth date)	2009- Dec 2016	No
Scottish Morbidity Record (SMR 01)	ICD-10 codes	2009- Dec 2016	No
Scottish Morbidity Record (SMR 01)	OPCS-4 codes	2009- Dec 2016	No
Scottish Morbidity Record (SMR 01)	Duration since index operation (date of admission from readmission - date of admission from index operation)	2009- Dec 2016	No
Scottish Morbidity Record (SMR 01)	Details of operation - laparoscopic/ open	2009- Dec 2016	No
Scottish Morbidity Record (SMR 01)	End of follow-up (month) (Date of end of follow-up, typically June 2016; however some patient might not complete follow-up because of mortality or migration)	2004- Dec 2016	No
Scottish Morbidity Record (SMR 01)	Continuous Inpatient Stay	2009- Dec 2016	No
CHI Database	Migration Month / year	2004- Dec 2016	No

NRS Deaths	Patient alive or death by end of follow-up	2004- Dec 2016 (measured in months, no date provided)	No
------------	--	---	----

Please justify your need for identifiable or potentially identifiable variables:

Identifiable data is only needed during the processing of data. Data will be collected during a range of 5 years from index surgery. Patients with a relevant OPCS-4 code as listed in the appendix are selected, if no prior such operation was found in the five years previous to the index operation. Identifiable information, NHS number and birth date are needed during processing to select reoperations that are definitely or potentially related to adhesion in patients following their index surgery. After processing these data can be removed. Age is potential risk factor for adhesions and will therefore be calculated.

4.4	NRS/NHSCR Data Sources Please read section 4.4 of the guidance	
Complete this section if access to NHSCR is required, or if there is any National Records of Scotland involvement		
4.4.01	Does the proposal require access to NHS Central Registry as a sampling frame for cohorts?	No
4.4.02	Does the proposal involve flagging of individuals on the NHSCR for long term follow up?	Choose an item.
4.4.03	If yes, is flagging necessary: 
 
 To trace and contact individuals throughout the UK?
 
 To be informed of fact and cause of death?
 
 To be informed of the incidence of on-going cancers?
 
 To be informed of emigrations prospectively and retrospectively?
 
	
4.4.04	Is any other NRS involvement required?  Please provide details	

4.5	Making Contact with Individuals Please read section 4.5 of the guidance	
4.5.01	Is any direct contact with any group of individuals required? If Yes, please provide details below	No
Contact Group and Method of contact		Contact by (whom)

 Hospital Consultants	 Letter	 Phone	 Other (specify) :	
 Other NHSS Staff	 Letter	 Phone	 Other (specify) :	
 General Practitioners	 Letter	 Phone	 Other (specify) :	
 Patients/Public	 Letter	 Phone	 Other (specify) :	
 Relatives of participants	 Letter	 Phone	 Other (specify):	
 Others (please specify):	 Letter	 Phone	 Other (specify) :	
4.5.02	Please explain why contact is being made – append copies of relevant correspondence as supporting evidence			
	If applicable			

4.6 Community Health Index (CHI) Database Please read section 4.6 of the guidance	
Complete this section if access to CHI Database is required Not applicable	
4.6.01	What monitoring and audit of the use of CHI is planned? Please provide details
4.6.02	What technical method will be used to access CHI (online read-only, download, other extract, anonymised extract, etc)? Please provide details

4.6.03	Have any risks been identified in the proposal which relate specifically to CHI?	
---------------	--	--

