	
To evaluate the impact of laparoscopic surgery on adhesion- related formation, we are planning to perform an update of the SCAR studies to recent years in which a large number of laparoscopic surgeries have been performed. Comparison of readmissions for adhesion- related complications after open and laparoscopic surgery will be made. The study will provide an estimate of the current burden of adhesion-related morbidity in Scotland, which could also serve as a model for the current burden in other European countries. Further such estimate can be used to model the impact of further implementation of anti-adhesion barriers on adhesion-related morbidity and healthcare costs in both Scotland and abroad.

3.1.08	
Provide a full, clear and concise outline of the proposal design, listing: data sources; sample size ; inclusion/exclusion criteria (eg involvement in trial/survey; health event, etc); relevant date range; need for identifiable or potentially identifiable data; requirement for a matched control cohort etc.
 
We intend to use the Scottish National Health Service record linkage capabilities. Inclusion criteria are all patients undergoing initial abdominal or pelvic surgery between June 2009 and June 2011. Selection will be made by OPCS-4 codes related to the admission. A list of relevant codes can be found in the appendix. We choose for these years to allow inclusion of an incident population in a time that laparoscopic surgery had already been implemented and that allows for 4 to 5-years of follow-up.
 
We will exclude patient who had had abdominal or pelvic operation in the 5 years before 2009, as pre-existing adhesions from this prior surgery might influence results. There are no further exclusion criteria.
 
For analyses patients will be grossly divided in three groups of anatomical location of the surgery: hindgut, female reproductive tract, and foregut or other. Within each group subgroups of laparoscopic and open procedures will be made.
 
We expect approximately 70,000- 100,000 patients to have had abdominal or pelvic surgery in the period June 2009- June 2011. Approximately 25,000 are expected to have had prior abdominal surgery in the previous 5 years. Thus, we expect an incident population of 45,000 to 75,000 to be included in the study.

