	
For the study we will analyse re-admission in the years following surgery that are directly related to adhesions, possibly related to adhesions, and readmission with surgery that might be complicated by adhesions. For this purpose we will need a patient identifier that allows to link readmissions to the initial surgery. The data can be anonymized so that the identifier represent just a random number. As baseline characteristics we will only require age and sex. No further potentially identifiable data such as birth date, postal code or NHS number is required.
 
From the initial admission with abdominal or pelvic surgery we need ICD- 10 codes and OPCS- 4 codes describing the type of surgery performed as well as information whether the operation was performed laparoscopic ally or open. This same set of information is needed for any readmission in follow-up. Further we need the time interval (in months) between the index operation and the readmission. Only readmissions coded by one or more relevant ICD-10 or OPCS-4 code need to be included.
 
For a readmission to be classified as directly related to adhesions, an explicit adhesion reference was required in the operative OPCS-4 or diagnostic ICD-10 coding. Adhesions might however not always be coded, especially not if readmission goes without surgery. For example, a conservative treated small bowel obstruction might only be coded as abdominal pain, nausea, and vomiting. Therefore we will define a broader set of operative codes and diagnostic codes that might indicate a possibly adhesion- related complication.
 
Data from follow-up is requested to the latest date from which a complete record can be extracted.

3.1.09	Does the proposal have implications for, or target, sensitive groups or vulnerable populations? Please give details
	No
3.1.10	Does the proposal seek to use information exclusively about deceased persons? Please give details
	No

3.1.11	Have any members of the public/lay representatives been involved in the proposal design? Please give details
	No
3.1.12	Has any peer review of the proposal been undertaken? Please give details (for example formal review by a peer organisation or funding body, informal internal review, review by a third party)
	Informal internal review has been performed within the Radboud University Medical Center, department of Surgery. The research proposal and internal funding for performing the study were approved.

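### No minimum interval is stated before a readmission counts, so early postoperative readmissions can enter the possibly adhesion-related class

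*Combined protocol and SAP*

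**What the plan says.** **Outcome.** Section 3.1.08 states: "we will analyse re-admission in the years following surgery that are directly related to adhesions, possibly related to adhesions". It adds a third class, readmission for surgery that adhesions might complicate.

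**Selection.** Readmissions are filtered by code: "Only readmissions coded by one or more relevant ICD-10 or OPCS-4 code need to be included". The only patient exclusion is recent prior abdominal or pelvic surgery, after which the section says "There are no further exclusion criteria".

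**Classes.** A directly related readmission needs an explicit adhesion code. The possible class exists because, in the plan's example, "a conservative treated small bowel obstruction might only be coded as abdominal pain, nausea, and vomiting". The response is: "Therefore we will define a broader set of operative codes and diagnostic codes that might indicate a possibly adhesion- related complication".

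**Clock.** Section 3.1.08 says "Further we need the time interval (in months) between the index operation and the readmission". Section 4.3 lists instead "Duration since index operation (date of admission from readmission - date of admission from index operation". The first origin is the operation and the second is the index admission. Section 4.3 lists neither an operation date nor a discharge date. It does list date of admission and Continuous Inpatient Stay, both available for analysis rather than for processing only. No rule for using Continuous Inpatient Stay is given.

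**Use.** Section 3.1.07 plans an open versus laparoscopic comparison and a current burden estimate, which is to feed models of anti-adhesion barriers and healthcare costs.

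**The concern.** Pain, nausea and vomiting soon after an abdominal operation have many causes other than adhesions, such as ileus, wound or anastomotic problems and constipation. A class designed to tolerate non-specific coding is therefore least specific in the first weeks, and nothing in the text keeps those weeks out or shows them separately.

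Two results are exposed:

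- **Burden.** Early readmissions unrelated to adhesions raise the possibly-related figure. Barriers could not prevent them, so they would also raise the benefit modelled from it.
- **Route comparison.** Equal contamination pulls the laparoscopic/open ratio towards 1. Unequal contamination shifts it even when there is no true difference. The direction is open: earlier discharge could raise early laparoscopic readmissions, and more early complications could raise open ones.

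The large cohort gives no protection, because it makes a small systematic difference easier to declare significant.

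**Working it through.** **1. The plan's own figure.** Section 3.1.08 expects 70,000 to 100,000 operated patients and removes about 25,000. 70,000 − 25,000 = 45,000 and 100,000 − 25,000 = 75,000, which reproduces the stated incident population. There is no power calculation and no early readmission rate.

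**2. Share of the class that is early.** Assumptions: later possible-class readmission p = 10% or 15%; early readmission with a qualifying code e = 2% or 4%. If early and late patients do not overlap, the total is p + e. If each patient is counted once and the two risks are independent, it is p + (1 − p)e.

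| p | e | Total, no overlap | Early share | Total, counted once | Early share |
|---|---|---|---|---|---|
| 10% | 2% | 12% | 16.7% | 11.8% | 15.3% |
| 10% | 4% | 14% | 28.6% | 13.6% | 26.5% |
| 15% | 2% | 17% | 11.8% | 16.7% | 10.2% |
| 15% | 4% | 19% | 21.1% | 18.4% | 18.5% |

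The range is about 10 to 29%. In patients, 2% of 45,000 is 900 and 4% of 75,000 is 3,000 with an early event.

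**3. Route ratio (laparoscopic/open) with no true difference.**

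- Early 4% laparoscopic, 2% open, no overlap: (10 + 4)/(10 + 2) = 1.17 and (15 + 4)/(15 + 2) = 1.12. Counted once: 13.6/11.8 = 1.15 and 18.4/16.7 = 1.10.
- Reversed, no overlap: 12/14 = 0.86 and 17/19 = 0.89. Counted once: 11.8/13.6 = 0.87 and 16.7/18.4 = 0.91.
- A milder gap, 2% laparoscopic and 3% open, counted once: p = 10% gives 11.8/12.7 = 0.93; p = 20% gives 21.6/22.4 = 0.96.

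**4. Equal contamination with a true difference.** True risks 10% open and 7% laparoscopic (ratio 0.70), early 3% in both: open 0.10 + 0.90 × 0.03 = 0.127; laparoscopic 0.07 + 0.93 × 0.03 = 0.0979; observed ratio 0.77.

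**5. Chance of a spurious significant difference.** Assumptions: no true difference, early 3% open and 2% laparoscopic, p = 10% or 20%, laparoscopic share 20 to 40%, two-sided 0.05. Chance = Φ((Δ − 1.96 × SE0)/SE1), where SE0 uses the pooled proportion and SE1 the separate ones.

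- N = 45,000, share 20%, p = 20%: (0.008 − 1.96 × 0.00490)/0.00486 = −0.33, giving 37%.
- N = 75,000, share 40%, p = 10%: (0.009 − 1.96 × 0.00245)/0.00244 = 1.72, giving 96%.
- Over all combinations: 37 to 81% at 45,000 and 56 to 96% at 75,000.

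**6. Time at risk by route.** A patient still in hospital cannot be readmitted. Assume open index stays are 1 to 10 days longer.

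- Over 4 years: 1/1,461 = 0.07% to 10/1,461 = 0.68% of follow-up. Over 5 years: 0.05% to 0.55%.
- Stays of 15 days open and 5 days laparoscopic over 4 years: (1,461 − 5)/(1,461 − 15) = 1.007.
- Within 30 days of admission only: stays of 4 and 1 days give 29/26 = 1.12; stays of 15 and 5 days give 25/15 = 1.67.

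Unequal time at risk is negligible over the planned follow-up. It matters only inside a short early window.

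**The case against.** The strongest reply is that this is a data-access application, not the full protocol. Section 7 lists a code appendix and the protocol sent to the ethics board, and neither is in the supplied text. The symptoms in section 3.1.08 are an example, and the broader code set is still to be defined. This stands. A reader might infer that early readmissions for pain or vomiting will be counted, but the text supports only that they can be. A minimum interval may also exist in the unsupplied protocol.

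A second reply is that the ratios of 0.86 to 1.17 follow from choosing a two-fold difference in early readmission. This also stands, and the milder 3% versus 2% case gives 0.93 to 0.96. Some early symptom-coded readmissions will be genuine adhesive obstruction, so the early shares are upper bounds on contamination for the inputs used.

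A third reply is that the possible class is openly labelled as non-specific and reported beside a directly related class that needs an adhesion code. That limits the problem mainly to the possible class. It does not help a reader who must judge how much of that class arose in the first weeks.

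A fourth reply is that the study updates the earlier SCAR work, for which section 3.1.07 quotes 34.6% over 10 years, directly or possibly related. Removing early readmissions from the main figure could break that comparison if the earlier work had no cut-off, which the documents do not say. This argues for a sensitivity analysis, not a changed main figure.

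None of these replies supplies the missing timing rule or reconciles the two time origins.

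**Conclusion.** The point holds and should be acted on. In the supplied text the clock has two different origins, no minimum interval is set, and a deliberately broad class is filtered by code alone. Early postoperative readmissions can therefore enter the burden estimate and the route comparison.

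The size rests wholly on assumed rates: roughly 10 to 29% of the possible class, and a null ratio moved to about 0.86 to 1.17 if early rates differ two-fold.

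Three stronger readings are not supported:

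- **Unequal time out of hospital distorts the comparison.** The documents give no stays by route, and under the assumed stays the effect is below 1% over 4 to 5 years.
- **The route comparison is biased in a known direction.** Nothing in the documents gives early readmission by route.
- **The intervals exist only in months.** Section 3.1.08 asks for months, but section 4.3 makes admission dates available for analysis, so days can be derived.

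**What to change.** 1. Reconcile sections 3.1.08 and 4.3 and state one time origin.
2. State that records within the same Continuous Inpatient Stay as the index operation are not readmissions.
3. Derive the interval in days from the admission dates already requested.
4. Keep the all-readmissions figure for comparison with the earlier SCAR estimate.
5. Report early readmissions as a separate row for every class, including readmission for surgery that adhesions might complicate. One workable window is 30 days from the end of the index stay. The number is a convention to be fixed before the results are seen, not one the documents supply. If the end of the stay is unavailable, count from index admission and note that time at risk within that window may differ by route.
6. Repeat the possibly-related burden figure and the laparoscopic/open comparison without the early readmissions.
7. If the code appendix or the ethics-board protocol already holds a timing rule, cite it here.

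**Cost.** One table row and one sensitivity analysis. The end date of the stay may not be in the extract, and section 3.3.01 ties current access to questions on data presentation, so adding a variable may not be simple. The fallback in step 5 avoids that. Some genuine early adhesive obstructions drop out of the sensitivity figure but stay visible in the early row.

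### The only exclusion criterion, prior abdominal or pelvic surgery, has a fixed calendar window in item 3.1.08 and a rolling window in section 4.3, and the two select different cohorts

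*Combined protocol and SAP*

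**What the plan says.** Item 3.1.08 sets the inclusion: "Inclusion criteria are all patients undergoing initial abdominal or pelvic surgery between June 2009 and June 2011". It then sets the exclusion: "We will exclude patient who had had abdominal or pelvic operation in the 5 years before 2009". The reason given is that adhesions left by earlier surgery could affect the results, and the item states that nothing else excludes a patient. It describes the choice of years as made "to allow inclusion of an incident population", and it sizes the exclusion thus: "Approximately 25,000 are expected to have had prior abdominal surgery in the previous 5 years".

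Section 4.3, in the text under the variable table, gives the selection rule again with a different anchor: a patient with a relevant OPCS-4 code is selected "if no prior such operation was found in the five years previous to the index operation".

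The same table dates the variables. One row reads "Date of admission 2004- Dec 2016" and another "OPCS-4 codes 2009- Dec 2016". CHI also starts in 2004 and is marked as processing-only. The OPCS-4 row is marked as not processing-only, and there is no OPCS-4 row for 2004 to 2008.

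**The concern.** A window tied to the calendar and a window tied to each patient's index date cannot stay aligned over a two-year accrual period. A programmer who follows item 3.1.08 and one who follows section 4.3 will build different cohorts. On the plan's own figures this exclusion removes about 25,000 of 70,000 to 100,000 operated patients, so it shapes the denominator of every readmission rate.

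The disagreement also depends on the index date. Under the fixed rule, a patient who enters late is screened for surgery much further back than five years. Whether that touches the laparoscopic versus open comparison depends on how the mix of approaches changed over the two years, which the documents do not give.

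A smaller matter is that operations are identified by OPCS-4 code, and the code years in the table do not reach back over either look-back window.

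**Working it through.** **The plan's own figure.** From item 3.1.08: 70,000 − 25,000 = 45,000 and 100,000 − 25,000 = 75,000. The stated incident cohort of 45,000 to 75,000 reproduces. The 25,000 is 36% of the lower total and 25% of the upper. This arithmetic does not show which window was used.

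**Inputs.** Index months June 2009 to June 2011, which is 25 months (item 3.1.08). Rolling window: the 60 months before the index (section 4.3). Fixed window: 60 months, with two readings of item 3.1.08:
- Reading A: January 2004 to December 2008 (before the calendar year 2009).
- Reading B: June 2004 to May 2009 (before accrual opens in June 2009).

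**Overlap.** Let k be the number of months from June 2009 to the index, k = 0 to 24. The rolling window starts k months after June 2004.
- Months shared: 55 − k under A, 60 − k under B.
- Months only in the fixed window: 5 + k under A, k under B. All lie more than five years before the index.

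| Index | Rolling window | Shared, A | Shared, B | Fixed only, A | Fixed only, B |
|---|---|---|---|---|---|
| June 2009 (k = 0) | Jun 2004–May 2009 | 55 | 60 | 5 | 0 |
| June 2010 (k = 12) | Jun 2005–May 2010 | 43 | 48 | 17 | 12 |
| June 2011 (k = 24) | Jun 2006–May 2011 | 31 | 36 | 29 | 24 |

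**Months only in the rolling window.** These also number 5 + k under A and k under B, but k of them fall from June 2009 onward. A qualifying operation in those months is itself the patient's initial operation within accrual, so it is the index and not a missed prior operation. Subtracting k leaves 5 months under A (January to May 2009) and 0 under B, whatever the index date.

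**Examples.** An operation in March 2005 before a June 2011 index is 75 months earlier: excluded by the fixed rule on either reading, kept by the rolling rule. An operation in February 2009 before a June 2010 index is 16 months earlier: excluded by the rolling rule and by reading B, kept by reading A.

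**Code years.** If the listed OPCS-4 range starts in January 2009, it covers 5 + k months of the rolling window (5 of 60 for June 2009, 29 of 60 for June 2011). It covers 0 of 60 months of the fixed window under A and 5 of 60 under B. Full coverage needs codes from January 2004 (A) or June 2004 (B and rolling).

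**The case against.** **Item 3.1.08 may be loose wording for the rolling rule.** Its reference to initial surgery, its incident-population aim and its count of surgery in the preceding five years all point that way. This is a fair reading and a good reason to settle on the rolling window. The sentence that states the exclusion still names a calendar year, and it is the sole exclusion, so it needs correcting.

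**The fixed rule does not admit much earlier surgery.** A reader might infer that it lets in patients operated on up to 29 months before the index. The inclusion criterion does not support that: with initial surgery as the entry event, the gap is 5 months at most and may be nil. What grows with the index date is exclusion of older surgery. That shrinks the cohort but does not bring in the adhesions that the exclusion is meant to keep out. This objection stands, and it limits the finding.

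**The code years prove little.** A reader might infer from the table that the look-back could not have been run, or that many patients with prior surgery were missed. The documents do not support either. Sections 4.2 and 5.1.02 place linkage and anonymisation with controllers who already hold the records, and section 4.3 describes selection alongside the processing step ("Identifiable data is only needed during the processing of data"). The OPCS-4 row can be read as the codes to be released. Nor is the table a dependable list of processing inputs: birth date is said to be needed for processing but has no row of its own, and the end-of-follow-up and death rows start in 2004 although no index precedes June 2009. This part is therefore a clarification only. No passage, however, states that the controller screened on earlier codes.

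**Unseen papers.** The IRB protocol and the code appendix listed in Section 7 are not among the documents and may state the rule.

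**Conclusion.** The conflict is real. Followed literally, item 3.1.08 and section 4.3 apply different windows: they share 55 of 60 months for a June 2009 index and 31 for June 2011 under reading A, or 60 and 36 under reading B. The fixed rule fails to exclude prior surgery only in January to May 2009 (5 months under A, none under B). It wrongly excludes, relative to the rolling rule, patients with surgery more than five years before the index, over a span of 5 to 29 months (A) or 0 to 24 months (B).

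This rests on whole-month counting, on the two readings of the fixed window, and on *initial* making any qualifying operation from June 2009 onward the index. The number of patients affected cannot be derived from the documents, and nothing in them shows that the reported results are wrong. The mismatch in code years is a gap in the table, not evidence that the screen was not done.

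**What to change.** 1. **Confirm first.** Ask the data controller which window and which OPCS-4 code years were applied to the extract, and report the number excluded. Item 3.3.01 shows the project is already answering journal questions, so the text must end up matching what was done.
2. **Align the wording.** Use the rolling five-year window of section 4.3 in item 3.1.08, where it fits the incident-population aim and the count of prior surgery. If the fixed window was in fact applied, describe it as such. Then either rerun with the rolling window, or report it as a deviation with a sensitivity analysis, for example one limited to early index months, where the two windows differ least.
3. **Clarify the table.** In section 4.3, show OPCS-4 codes for 2004 to 2008 as processing-only and state that the controller applies the exclusion before release, if that is confirmed.

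Cost: if the rolling look-back was applied, one query, one sentence and one table row. If the fixed window was applied, a disclosed deviation and a sensitivity analysis, or a new extract and a rerun. If no adequate look-back was applied, a new extract and a rerun of the analysis.
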